### 10.3. Clinical Laboratory Tests

All treatment-emergent abnormal values as determined based upon the normal values provided by the central laboratory will be listed with relevant patient information. In addition, for those tests that have potentially clinically significant (PCS) criteria, all PCS treatment-emergent values will be identified. The following PCS criteria will be used:

Clinical Chemistry Variable	PCS Criteria
Albumin	<2 g/dL
Alkaline phosphatase	> 5.0 – 20.0 x ULN*
Amylase	>2.0 – 5.0 x ULN
Calcium	<7.0 – 6.0 or >12.5 – 13.5 mg/dL
Carbon dioxide	<11 – 8 mmol/L
Cholesterol (total)	>400 – 500 mg/dL
Creatinine	>1.5 x ULN
Potassium	<3.0 - 2.5 or >6.0 - 7.0 mmol/L
PRA	> 20%**
Serum aspartate aminotransferase [SGOT (AST)]	>5.0 – 20.0 x ULN
Serum alanine aminotransferase [SGPT (ALT)]	>5.0 – 20.0 x ULN
Sodium	<130 - 120 or >155 - 160 mmol/L
Total bilirubin	>3.0 – 10.0 x ULN
Hemoglobin (urine)	Present
Albumin (urine)	>30 or 300 mg/24 hrs depending on baseline level***
Total protein (urine)	1.0 – 3.0 g/24 hrs

Clinical Chemistry Variable	PCS Criteria
Hemoglobin	< 8.0 – 6.5 g/dL
WBC Neutrophils/granulocytes	<1.0 – 0.5 x 10  /L
Platelets	<50 – 25 x 10  /L

\*LLN=Lower Limit of Normal; ULN=Upper Limit of Normal

\*\*Post allogeneic transplant

\*\*\*See safety endpoints in Section 2.7.1b.

For hematology and clinical chemistry laboratory parameters, actual values at Baseline and each follow-up visit will be summarized. The change from baseline values will be summarized at each visit. If repeated samples are performed for any scheduled time point, the first non-missing assessment for that time point will be used in these analyses.

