### **10.1. Adverse Events**

An adverse event is any unfavorable and unintended diagnosis, symptom, sign (including an abnormal laboratory finding), syndrome, or disease that either occurs during the study, having been absent at baseline, or if present at baseline, appears to worsen.

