#### **10.1.1. Definitions**

The following definitions will be applied consistently to the safety analysis:

Baseline (Clinical Labs, Physical Examinations)	The baseline value will be the result collected at the immediate pre-transplant work-up visit, if scheduled, or the most recent screening visit prior to the islet transplant where the lab/examination was scheduled.
Baseline (Vital Signs)	The baseline value will be the result collected at the immediate pre-transplant work-up visit. If this assessment was not obtained, then the most recent value obtained for

	the specific parameter prior to the islet infusion will be used as the baseline value.
Baseline (ECG parameters)	The baseline value will be the most recent pre-transplant value obtained.
Change from baseline	Value at the time point – value at baseline
Treatment-emergent	Any safety assessment that occurred at the onset of or after start of the first islet infusion, up to the end of 1-year follow-up after the last infusion.

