#### 10.1.5. Analyses of Adverse Events

Adverse events will be coded to the Medical Dictionary for Regulatory Activities (MedDRA) preferred terms (PT) and system organ classes (SOC) using version 17.0 or higher. All tabular AE summaries will be for treatment-emergent adverse events (TEAE). For all percentages, the number of patients in the ITT population will comprise the denominator.

An overall summary table will be developed to report, across the total safety population and by number of transplants received, starting from the day of first islet cells infusion to the end of 1-year follow-up after the last transplant, the total number of events and the number and percent of patients having at least one event and those related to treatment in the following categories:

a. Procedure Related Events

The incidence and severity of adverse events related to the islet infusion procedure including:

- Bleeding (> 2 g/dl decrease in hemoglobin concentration) identified within 24 hours post transplant.

- Portal vein thrombosis, branch or main, detected by ultrasound by the end of Day 7 (or on the first visit post-transplant if it does not fall on Day 7 exactly).
- Biliary puncture identified within 24 hours post transplant.
- Wound complication (infection or subsequent hernia) identified by the end of Day 7 (or on the first post-transplant visit if it does not fall on Day 7 exactly).
- Increased transaminase levels (> 5 times upper level of normal) identified by the end of Day 30 (or on the post-transplant visit that is closest to Day 30 if it does not fall on Day 30 exactly).

b. Immunosuppression/study drug Related Events

The incidence and severity of adverse events related to immunosuppression and/or the study drug (islets), including:

- Allergy
- Reduction in GFR (> 25% reduction in estimated GFR from baseline by Cockcroft and Gault formula:

$$eC_{Cr} = \frac{(140 - \text{Age}) \times (\text{Weight in kilograms}) \times [0.85 \text{ if Female}]}{72 \times (\text{Serum Creatinine in mg/dL})}$$

- Increase in urinary albumin excretion
- New onset microalbuminuria (albumin > 30 mg/day confirmed by 24 hour urine collection) in patients who were previously within normal limits
- For those patients with baseline microalbuminuria (30-300 mg/day), new onset overt albuminuria (greater than 300 mg/day confirmed by 24 hour urine collection)
- Sensitization evidenced by increase in PRA by at least 20% relative to baseline

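### SAP 10.1.5 does not say whether its 20% rise in PRA is a ratio or percentage points; taken literally it counts 10 to 12 as sensitization and gives no result at a baseline of 0%

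*SAP*

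**What the plan says.** SAP 2.9 restores PRA, which the protocol's safety list had left out, and calls it critical for safety. Two rules then act on it.

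The first is in SAP 10.1.5, in the list of events related to immunosuppression or the islets: "Sensitization evidenced by increase in PRA by at least 20% relative to baseline". For the categories in that section the SAP plans "the total number of events and the number and percent of patients having at least one event and those related to treatment". SAP 10.1.1 defines change from baseline as "Value at the time point – value at baseline". The Table 14.3.16 shell reports PRA in percent, actual and change, separately for Class I and Class II.

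The second is in SAP 10.3, which says that "for those tests that have potentially clinically significant (PCS) criteria, all PCS treatment-emergent values will be identified". The PRA criterion there is a value above 20%, with the single footnote "Post allogeneic transplant". SAP 10.1.1 defines treatment-emergent by timing alone: "Any safety assessment that occurred at the onset of or after start of the first islet infusion", up to one year after the last infusion. In the same table the urine albumin criterion does use baseline: ">30 or 300 mg/24 hrs depending on baseline level". The flag is reported in Table 14.3.18, a listing with a column for the baseline result.

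On entry, item 21 of protocol section 6.4.2 excludes a positive Class I solid-phase result or a general panel PRA above 80%. Protocol 6.5.2 provides Thymoglobulin induction for sensitized patients, so some pre-existing antibody is expected.

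**The concern.** For a measure already expressed in percent, a 20% increase relative to baseline can mean multiplication by 1.2 or the addition of 20 points. These are different events. The GFR line in the same SAP 10.1.5 list is a percent reduction in the ordinary ratio sense, so a programmer working down the list could reasonably code PRA the same way.

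Under the ratio reading the rule is easiest to meet where antibody is lowest and matters least. It has no value at a baseline of 0%, which is where new sensitization would be clearest. What is at stake is which subjects are recorded as sensitized on a measure that the SAP itself singles out.

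The SAP 10.3 row raises a smaller matter. A subject who enters with PRA above 20% and never changes is marked as having a treatment-emergent, potentially clinically significant (PCS) result.

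**Working it through.** The plan gives no figure here to reproduce, so the check applies the rules as written. Let b be baseline PRA and v post-transplant PRA, in whole percent. I take b from 0 to 80, which assumes that the item 21 general-panel ceiling applies to the value later compared with follow-up, and v from 0 to 100.

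- Ratio reading: (v − b)/b ≥ 0.20, that is v ≥ 1.2b for b > 0.
- Points reading: v − b ≥ 20.
- SAP 10.3 now: v > 20.
- SAP 10.3 with a baseline condition: v > 20 and v > b.

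**Thresholds for sensitization**

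| Baseline b | Ratio trigger (1.2b) | Rise needed | Points trigger (b + 20) |
|---|---|---|---|
| 0% | undefined | – | 20% |
| 5% | 6% | 1 point | 25% |
| 10% | 12% | 2 points | 30% |
| 30% | 36% | 6 points | 50% |
| 80% | 96% | 16 points | 100% |

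**Baseline 0%.** For 0 to 60 the percent change is (60 − 0)/0, which a program would normally return as missing and so not count. If the rule is coded as v ≥ 1.2b instead, the condition becomes v ≥ 0. Any rise then counts, and so does 0 to 0 unless a rise is required separately. The result depends on the coding.

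**How far the two readings differ.** For b from 1 to 80, the values that meet the ratio but not the points reading run from b + ⌈b/5⌉ to b + 19, which is 20 − ⌈b/5⌉ values. Summed: 80 × 20 − 5 × (1 + … + 16) = 1,600 − 680 = 920 pairs. The reverse needs b + 20 < 1.2b, so b > 100, and there are none. At nonzero baselines, stating points can only remove events. At 0% it supplies a result where the percent change has none.

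**SAP 10.3.** Pairs flagged with no rise (v > 20 and v ≤ b) number b − 20 for each b from 21 to 80: 1 + … + 60 = 1,830. All flagged pairs number 81 × 80 = 6,480. Adding v > b removes exactly those 1,830 and leaves 6,480 − 1,830 = 4,650, all of them rises.

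These are counts of possible values that test the rules. They are not patient frequencies.

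| Baseline to follow-up | 10.3 now | 10.3 with v > b | 10.1.5 ratio | 10.1.5 points |
|---|---|---|---|---|
| 10 to 12 | no | no | yes | no |
| 5 to 24 | yes | yes | yes | no |
| 30 to 45 | yes | yes | yes | no |
| 60 to 79 | yes | yes | yes | no |
| 0 to 60 | yes | yes | undefined | yes |
| 80 to 100 | yes | yes | yes | yes |
| 30 to 30 | yes | no | no | no |
| 50 to 40 | yes | no | no | no |

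**The case against.** The sponsor could say that percentage points are obviously meant, given the SAP's definition of change and the layout of Table 14.3.16. I think that is probably the intention. But the rule does not say so, its literal wording points the other way, and it does not say whether either class suffices. What remains is a correction to the wording of an event definition, worth making before analysis.

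The points rule also gives something up. Rises such as 5 to 24 or 30 to 45 are no longer sensitization events, and neither document gives a clinical basis for 20 points. That stands. The figure of 20 is the plan's own, and the smaller rises remain in the change columns of Table 14.3.16.

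On SAP 10.3, the requirement that a finding be new, "having been absent at baseline, or if present at baseline, appears to worsen", defines an adverse event and not a laboratory screen. Most rows of that table are fixed levels without a baseline condition. The listing prints the baseline result, and Table 14.3.16 shows change by class. All of this stands and keeps the point secondary. What survives is that the protocol can admit subjects already above the PRA cut-off. It likewise admits microalbuminuria, and there the criterion was tied to baseline.

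A reader might infer that each subject classified differently by the two readings moves a reported percentage by 1/50 = 2.0 points. The documents do not support this. SAP 10.1.5 plans percentages of patients with at least one event by category, and sensitization shares its category with anemia, neutropenia, infections and others. The protocol's table of Phase 1/2 adverse events shows anemia in 10 of 10 subjects and neutropenia in 7 of 10, so most subjects would probably be counted in that category anyway. The Table 14.3.1 shell has no sensitization row, and SAP 2.8 discusses results with as few as 15 patients.

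**Conclusion.** The concern holds in a limited form and is minor. The sensitization threshold in SAP 10.1.5 is not usable as literally written: its trigger runs from 1 point at a baseline of 5% to 16 points at 80%, and a percent change does not exist at 0%. Percentage points agree with the rest of the SAP.

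The baseline-0% problem would be common if follow-up Class I PRA uses the solid-phase assay of item 21, because eligible subjects would then start at 0%. That is an assumption, since the documents name no follow-up assay.

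The SAP 10.3 observation is accurate but confined to a listing. A reader might infer that it inflates a reported rate of new antibody, but no rate of PRA PCS results is planned. The number of subjects with raised baseline PRA is not given, so no effect in patients can be stated. The primary analysis is unaffected.

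**What to change.** In SAP 10.1.5, restate the rule as: *increase in PRA of at least 20 percentage points from baseline, Class I or Class II*, with baseline as already footnoted in Table 14.3.16 (last value before the first infusion). An event stays possible at the 80% entry ceiling (80 to 100).

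Optionally, in the SAP 10.3 PRA row: *above 20% post-transplant and above the subject's baseline*. This clears unchanged and falling values and costs no rise its flag. I would not require a 20-point rise there for subjects already above 20%. That would remove the flag from rises of 1 to 19 points, such as 60 to 79, which would then have neither a flag nor a sensitization event.

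The cost is one SAP line, or two with the option. PRA is already scheduled and tabulated by class against baseline, so no test, visit, patient or protocol amendment is needed.

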#### **10.4. Vital Signs and Other Observations Related to Safety**

##### **10.4.1. Vital Signs**

The vital sign parameters will include heart rate, systolic blood pressure (SBP), diastolic blood pressure (DBP), respiration rate, and temperature. All PCS treatment-emergent vital sign values will be listed with relevant patient information. The PCS values will be identified based on the following criteria:

Vital Sign Variable	PCS Criteria
Systolic Blood Pressure	>150 mmHg or an increase of $\geq 20$ mmHg <90 mmHg or a decrease of $\geq 20$ mmHg
Diastolic Blood Pressure	>100 mmHg or an increase of $\geq 20$ mmHg <50 mmHg or a decrease of $\geq 15$ mmHg
Heart Rate	>120 bpm and an increase of $\geq 15$ beats/min <50 bpm and a decrease of $\geq 15$ beats/min

The actual vital sign values and the change from baseline values will be summarized at each scheduled time point post-transplant during the treatment and follow-up.

##### **10.4.2. Electrocardiogram (12-Lead)**

At each scheduled time point during the Treatment and Follow-up Phases up to the last assessment that is closest to Day 365  $\pm$  28 days with Day 0 being the day of last islet transplantation, the qualitative interpretation of the ECG results (normal, abnormal) will be analyzed by presenting the number and percentage of patients who worsened at that time

point. Worsening will be defined as a change from a rating of normal/abnormal not clinically significant on both of the pre-transplant assessments to abnormal clinically significant at the time of evaluation. All treatment-emergent worsening in ECG results will be listed with relevant patient information.

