6.6.3 Period on the Waiting List

During phase 3 of the screening period subjects are awaiting their first transplant and will have re-evaluations every 3 months (see Appendix *Detailed Visit Schedule*):

Tests scheduled every 3 months:

- HbA1C

- Comprehensive metabolic panel
- Microalbumin/creatinine ratio
- PRA

Tests scheduled if the subject has not been transplanted within 6 months:

- History and physical
- ECG
- Lab tests to be done in addition to the 3 months schedule
 - CBC
 - PT, PTT, INR
 - HIV
 - Hepatitis panel for hepatitis B and hepatitis C virus
 - VzV IgG if negative at screening phase 2
 - CMV if negative at screening phase 2
 - EBV if negative at screening phase 2
 - RPR
 - Lipid panel
 - Serum pregnancy test

The most recent values for these tests will be recorded in the pre-transplant records.

6.6.4 Immediate Pre-Transplant Work-Up (see Appendix Detailed Visit Schedule and Transplant Order)

Before the transplant the subject will be admitted to the Transplant Unit at the UIC Hospital and the following screening performed to ensure the subject is medically fit to undergo safely the transplant procedure:

- a. History and physical exam
- b. Laboratory studies - STAT
 - Hematology
 - CBC and differential
 - PT-INR, PTT
 - ABO type and cross match
 - Biochemistry
 - Total bilirubin, AST, alkaline phosphatase, albumin, total protein
 - Electrolytes, creatinine, glucose, BUN, magnesium, phosphorous
 - Urinalysis
 - Microbiology
 - Serum CMV IgG & IgM, EBV IgG & IgM
 - C&S and fungi: sputum, urine and blood on subjects who were in hospital during the past week
 - Serum pregnancy test

- Prospective donor-recipient cross match by flow and cytotoxicity sent from the Islet Processing Facility

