6.9 Adverse Events Definitions and Monitoring

6.9.1 Adverse Event (AE)

An adverse event is any unfavorable and unintended diagnosis, symptom, sign (including an abnormal laboratory finding), syndrome, or disease which either occurs during the study, having been absent at baseline, or if present at baseline, appears to worsen.

The length of time between screening and first transplantation may be 6 months or more. Therefore, non-serious adverse events will be recorded on the case report forms (CRF) for the period starting with hospitalization for the first transplantation and during the subsequent study period because these events are relevant to the islet cell transplantation. All serious adverse events (see below) regardless of time relative to transplantation will be recorded on the case report form

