	Week 1	X	XX	XX	XX	XX	XX	X	XX	XX	XX	XX	XX
	etc.												
2 Tx's (N=XX)													
Etc.													

[1] Baseline is always the value before the initial transplant.

[2] Day 1 assessments were obtained during 24 hours post-transplant during the Treatment Phase (in-clinic).

XXXXXXXXXX.sas, DDMMYYYY:HHMM

TABLE 14.3.23  
 Listing of Vital Signs for Patients with PCS Treatment-Emergent Results

# of Tx Received	Subj. No.	Age (yrs.)	Timepoint	Vital Sign Parameter	PCS? (Y=yes)	Timepoint Value	Baseline Value
1 Tx	XXX	XX	Day 1 30 min	SBP (mmHg)		XX	XX
				SBP (mmHg)		XX	XX
				HR (beats/min)	Y	XX	XX
			etc.				
	XXX	XX	Week 1	SBP (mmHg)		XX	XX
				SBP (mmHg)		XX	XX
HR (beats/min)				Y	XX	XX	
		etc.					
2 Tx	Etc.						

Note: Potentially Clinically Significant (PCS) Criteria:

SBP: >180 mmHg and an increase of >=20 mmHg OR <90 mmHg and a decrease of >=20 mmHg from baseline

DBP: >105 mmHg and an increase of >=15 mmHg OR <50 mmHg and a decrease of >=15 mmHg from baseline

HR: >120 beats/min and an increase of >=15 beats/min OR <50 beats/min and a decrease of >=15 beats/min

XXXXXXXXXX.sas, DDMMYYYY:HHMM

TABLE 14.3.24  
 Electrocardiogram - Worsening from Baseline to 1 Year Post Last Transplant

# of Tx Received	Number (%) [1] of Patients Who Worsened [2]		
	Post- Transplant Assessment Time		
	Total	Week 20	Week 52
Total (N=X) Worsened	X (XX)		
1 Tx (N=X) Worsened	X (XX)	X (XX)	X (XX)
2 Tx (N=X) Worsened	X (XX)	X (XX)	X (XX)
3 Tx (N=X) Worsened	X (XX)	X (XX)	X (XX)

[1] The denominator is the corresponding number of patients in the leading column.

[2] Worsening is defined as a change from a rating of normal/abnormal not clinically significant on both of the pre-transplant assessments to abnormal clinically significant at the time point.

XXXXXXXXXX.sas, DDMMYYYY:HHMM

TABLE 14.3.25  
Listing of Patients with Treatment-Emergent ECG Abnormalities

# of Tx Received	Subj. No.	Age (yrs.)	Timepoint	ECG Abnormality Description
1 Tx	XXX	XX	Week 20	XXXXXXXXXXXXXXXXXXXXX
			etc.	
2 Tx	XXX	XX	Week 52	XXXXXXXXXXXXXXXXXXXXX
			etc.	

Total number of patients with at least one event: N = XX

---

XXXXXXXXXXXX.sas, DDMMYYYY:HHMM

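### The ECG-worsening rule needs two pre-transplant ECGs, but the second is scheduled only after a six-month wait; coded as written, the reported rate is biased downward.

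*SAP*

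**What the plan says.** SAP 10.4.2 gives the rule: "Worsening will be defined as a change from a rating of normal/abnormal not clinically significant on both of the pre-transplant assessments" to abnormal and clinically significant at the time of evaluation. Note [2] of Table 14.3.24 repeats it ("not clinically significant on both of the pre-transplant assessments to abnormal clinically significant at the time point"), so the two-ECG condition, "on both of the pre-transplant assessments", is what a programmer would code. Note [1] of the same table sets the percentage base: "The denominator is the corresponding number of patients in the leading column". That means every patient in the row.

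The ECG row of the evaluation schedule (Protocol 6.6.8, repeated in SAP 17.1.1) has pre-transplant marks only at A1 and A3B. Protocol 6.6.3 lists ECG under "Tests scheduled if the subject has not been transplanted within 6 months", not among the three-monthly tests. The immediate pre-transplant work-up in Protocol 6.6.4, introduced as "the following screening performed to ensure the subject is medically fit to undergo safely the transplant procedure", names no 12-lead ECG.

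SAP 10.1.1 defines the ECG baseline as one value: "The baseline value will be the most recent pre-transplant value obtained".

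**The concern.** The worsening rule presupposes two pre-transplant ECGs for everyone, while the schedule guarantees only one. For a patient transplanted within six months, no scheduled second assessment exists for the condition to be tested on. The SAP has no rule for this case, and SAP 3.1 leaves missing data missing unless an imputation rule is given.

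If the rule is coded as written, such patients add to the denominator and contribute nothing to the numerator, whatever their later ECGs show. The error runs in one direction, towards a cleaner cardiac safety table, in a trial whose stated purpose (Protocol 6.2, SAP 2.1) is to support a biological license application. Two SAP sections can also classify the same patient differently.

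**Working it through.** The plan states no rate or sample size for ECG worsening, so there is no figure of its own to reproduce.

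**Step 1: the schedule.** Read against its 23 visit columns, the ECG row has marks at A1, A3B, visit 10 (week 20) and visit 18 (week 52). A3B corresponds to the six-month list in Protocol 6.6.3. A patient transplanted sooner therefore has one scheduled pre-transplant ECG. The wait varies: Protocol 6.9.1 says "The length of time between screening and first transplantation may be 6 months or more".

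**Step 2: the two rules side by side.** Call a rating of normal or abnormal-not-clinically-significant *benign* (B), and abnormal clinically significant *S*. Suppose the post-transplant ECG is S.

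| Pre-transplant ECGs | Benign on both (10.4.2, literal) | Benign on most recent (10.1.1 baseline) |
|---|---|---|
| B only | not counted | worsened |
| S only | not counted | not counted |
| B, then B | worsened | worsened |
| B, then S | not counted | not counted |
| S, then B | not counted | worsened |
| S, then S | not counted | not counted |

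The rules differ in two rows: patients with a single benign ECG, and patients whose earlier ECG was clinically significant but whose latest was not. In both rows the literal 10.4.2 rule gives the lower count.

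**Step 3: size.** Let f be the share of patients with only one pre-transplant ECG, and p the proportion who worsen relative to their most recent pre-transplant ECG. The documents give neither, so both are assumptions. If worsening is unrelated to waiting time, and leaving aside the uncommon S-then-B pattern:

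- reported proportion = p × (1 − f)
- relative understatement = [p − p(1 − f)] / p = f
- expected number reported = N × p × (1 − f)
- chance that the table shows no worsening = [1 − p(1 − f)]^N

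With the planned N = 50 and an assumed p = 10%:

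| f | Reported proportion | Expected number reported | Chance of none |
|---|---|---|---|
| 0 | 10% | 5.0 | 0.5% |
| 25% | 7.5% | 3.75 | 2.0% |
| 50% | 5% | 2.5 | 7.7% |
| 75% | 2.5% | 1.25 | 28% |
| 100% | 0% | 0 | 100% |

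For other values of p at f = 50%, the expected number falls from 2.5 to 1.25 if p = 5%, and from 10 to 5 if p = 20%.

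**Step 4: after the change.** With the single most recent ECG as baseline, every patient with a screening ECG has a baseline, so the factor (1 − f) disappears. The expected count at N = 50 returns to 2.5, 5 or 10 for p = 5%, 10% or 20%.

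**The case against.** The best defence is that the SAP is silent on the one-ECG case and does not exclude such patients from the numerator. SAP 10.1.1 introduces its definitions as applying throughout the safety analysis, so a programmer could fall back on the most recent value, or read the condition as all available ECGs, and no bias would follow. That is possible, but the text does not say it. The two-ECG wording appears in both the section and the table note. The precedence rule in SAP 3 ranks specific sections over its own general policies; it does not rank 10.1.1 against 10.4.2.

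A reader might infer four stronger things that the documents do not support:

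- *That early-transplanted patients can never be counted.* This holds only under the literal rule and with no unscheduled second ECG. Protocol 6.6.2 includes unspecified cardiac testing in screening phase 2, the schedule has a cardiology consult at A2, and the detailed visit schedule and transplant order appendices are not reproduced. A second ECG may exist for some of these patients. Continuous monitoring during the infusion would not serve as one.
- *That two normal ECGs are needed.* Abnormal but not clinically significant also qualifies.
- *That a definite understatement, such as 25% to 75%, can be stated.* That would only return an assumed share of early transplants as a result.
- *That the two SAP sections disagree generally.* They differ only in the two patterns shown above. The cardiac exclusions in Protocol 6.4.2 should make the S-then-B pattern uncommon.

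Other outputs also limit the loss. Table 14.3.25 lists ECG abnormalities with a patient count, Listing 16.2.9b gives ECG diagnoses, and a new clinically significant finding may reach the adverse event tables. These may show individual cases. They do not correct the rate in Table 14.3.24, and SAP 10.4.2 ties its own listing to the same notion of worsening. SAP 3.4 calls for a missing category, but the Table 14.3.24 shell has none.

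**Conclusion.** The point stands as an inconsistency with a one-directional effect. The numerator rule needs two pre-transplant ECGs, the schedule provides the second only after a six-month wait, and the denominator keeps everyone. Coded as written, this can only lower the reported worsening rate. The relative understatement equals the share of patients with one pre-transplant ECG. That result assumes literal coding and worsening unrelated to waiting time. If worsening does depend on waiting time, the loss is instead the share of true cases arising among one-ECG patients. The documents do not give the share, so no single figure can be attached.

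The impact is modest. ECG worsening is descriptive, carries no test or decision rule, and is not among the safety parameters that SAP 2.7.1 names as being of primary interest.

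**What to change.** In SAP 10.4.2, define worsening as a change from normal or abnormal-not-clinically-significant on the most recent pre-transplant ECG, as in 10.1.1, to abnormal clinically significant at the time point. Use as denominator the patients with a baseline ECG and an ECG at that post-transplant time point. Revise note [1] (denominator) and note [2] (definition) of Table 14.3.24 to match.

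The cost is wording in one SAP section and two table notes, made before programming. It needs no new data, no added visit and no protocol amendment.
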